- c) To assess the effect in the level of PSA, if any.
- d) Exploring Siddha clinical parameters of the clinical condition *Purasthakola perukkam* [BPH].

2. Study Design:

[figure not shown]
Open clinical study

[Randomized, comparative open labeled clinical study]

Since the trial is in two arms, to avoid the bias in the study participants, randomization is opted. The efficacy will be compared with the known Siddha drug XXX. The indication tried with that of XXX is a novel idea, Henceforth the baseline study will be of open labeled.

The expected total duration of subject participation will be six months. Data summarization, Statistical analyzing and monograph preparation will need additional three months. The drug therapy will be of 12 weeks. The follow up will be done without drug on 45th day and 90th day.

3.1 Study design schematic:

3.2 Allocation to treatment:

This clinical study involves two arms. The sample size of subjects is 20. 10 subject each in a single arm. They will be randomized by appropriate method.

3.3 Breaking the blind:

Blinding is not opted as both the trial drugs are classical preparations. The making of placebo is little bit difficult. The study comes under Phase II category. There is lack in published data. Hence an open clinical study is designed.

4. Subject selection:

The proposed clinical evaluation of the investigational new drugs will be done in the OPD's of peripheral Institutes of CCRS. The estimated total number of individuals to be enrolled in this clinical study will be twenty. The subjects to be enrolled will be provided with patient information sheet and informed consent form.

4.1 Subject inclusion criteria:

- Male patients between 40 and 75 years of age.
- Patient diagnosed with BPH and with clinical signs and symptoms of BPH for 3 months.
- Confirmed diagnosis: a) Ultra sonogram study
b) Prostatic Specific Antigen Score 4 ng to 8 ng /mL
[Normal range-PSA Score 0.8 to 4 ng /mL]
- Patient having a post-void residual urine volume of 350 cc.
- Participants who adhere to protocol requirements with written informed consent.

4.2 Subject exclusion criteria:

- PSA score beyond acceptable range and patients with a history of prostate cancer or a serum PSA >8 ng/mL [will be excluded by reviewing the past medical history and the current medication]
- History of urinary urethral obstruction due to stricture, valves, sclerosis or tumor at initiation
- Clinical evidence of prostate cancer at initiation

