5.1.1 Withdrawal of subjects due to non-compliance / adherence

During the course of the trial study period if any serious condition develops which requires urgent treatment such subject may be withdrawn from the trial and managed by the principal investigator accordingly.

5.2 Study drug supplies:

Drugs will be procured from SCRI, Chennai. In case, if there is any difficulty, direction may be given to purchase the trial drugs from any GMP certified firms.

5.2.1 Formulation and packaging:

Each drug will be packaged in the packing paper or polythene cover according to the said dosage. It will be given for 15 days. The review of the participants will be advised accordingly.

5.2.2 Mode of dispensing:

The study drugs will be kept in the co investigator's room and dispensed from there.

5.2.3 Drug administration:

Each study drug will be administered as investigator directed procedure. Specific instructions like do's and don'ts, foods which have to be avoided or added and drug compliance will be given to participant during each review.

5.4 Study drug storage and accountability:

Appropriate storage of the study drugs to ensure their stability will be observed by the investigators. Accountability of the study drugs are also done with documentation. Disposition or other destruction of the study drugs upon completion of the study will be done according to the instructions of the investigators.

5.5 Concomitant Medications:

If any infectious illness occurs to the study participants during the trial period, the concomitant medications will be advised by the investigators.

5.5.2 Rescue Medication:

If any problems occur, rescue medication will be governed by the investigators accordingly.

6. Research Study Procedures:

This study is a randomized, comparative, open-labeled comparing the safety and efficacy of XXX and XXX for 12 weeks in 20 patients with *Purasthakola perukkam* [benign prostatic hyperplasia]. The primary outcome measures will be validating the efficacy of interventional drug with comparator drug by change in Total International Prostate Symptom Score from baseline to end of treatment. The secondary outcomes will be evaluation of the safety of the investigational drug, Process Standardization and exploring Siddha clinical parameters of the clinical condition *Purasthakola perukkam* [BPH].

6.1. Screening procedures:

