The eligible participants will be enrolled according to the inclusion criteria. The full details of the history and physical examination of the patient will be recorded as per the Proforma (Form 1 & 2) Clinical Assessment will be done on 0, 15, 30,45,60,75 and 90th days (Form 3). Laboratory investigations will be recorded as per the proforma (Form 4) before treatment (0 day), after treatment (at the end of 3rd 6th and 9th month).

6.2 Study drug procedures:

The study arm 1 will receive 100mg of drug with milk q.s after food at morning and night.

The study arm 2 will receive 60 ml of decoction before food at morning and night.

6.3 Follow-up procedures:

Follow ups in both arms will be carried out after 45th and 90th day after completion of 3 months treatment period.

6.4. Schedule of activities (Study table):

Type of study	Randomized, comparative, open labeled clinical study									
Phase	2									
Sample size	20 [without including drop outs, lama]									
Randomization	By appropriate method									
Study arms	Arm 1 => 10 subjects					Arm 2 => 10 subjects				
Intervention	xxx – 100 mg bid with milk after food					xxx- 60 ml bid before food				
Study period	6 months [3 months drug therapy + 3 months follow up]									
Visits		At initial visit (0)	I visit (15 th day)	II visit (30 th day)	III visit (45 th day)	IV visit (60 th day)	V visit (75 th day)	VI visit (90 th day)	Follow up 6 th month	Follow up 9 th month
Arm 1	10 subjects	Screening	Measuring IPSS and other Clinical data	Reporting ADR if any	Reporting ADR if any					
Laboratory investigations		USG,PSA test and other investigations						USG,PSA test and other investigations		
Arm2	10 subjects	Screening	Measuring IPSS and other Clinical data	Reporting ADR if any	Reporting ADR if any					
Data compilation	Data compiled for preparing monograph. Research article will be communicated after compiling the data.									

Safety and Effectiveness Assessments:

7.1 Safety assessment:

Blood and Urine examination will be done to evaluate the safety of the study drug. Laboratory investigations will be recorded as per the proforma (Form 4) before treatment (0 day), after treatment (at the end of 3rd 6th and 9th month).

7.2 Effectiveness assessment:

The IPSS, ultra sonogram study and test for PSA range will be done according to the proforma.

8. Adverse Event Reporting:

8.1 Adverse event definitions:

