8.2 Recording / Reporting requirements

8.2.1 Eliciting adverse event information:

Participants will be routinely observed and questioned about adverse events during their visits.

8.2.2 Recording requirements:

All observed or volunteered adverse events (serious or non-serious) and abnormal test findings, regardless of study group or suspected causal relationship to the study drug(s) will be recorded in the subjects’ case histories. For all adverse events, sufficient information will be pursued and/or obtained so as to permit 1) an adequate determination of the outcome of the event (i.e., whether the event should be classified as a *serious adverse event*) and; 2) an assessment of the casual relationship between the adverse event and the study drug(s).

Adverse events or abnormal test findings felt to be associated with the study drug(s) will be followed until the event (or its sequelae) or the abnormal test finding resolves or stabilizes at a level acceptable to the Sponsor-Investigator.

8.2.2.1 Abnormal test findings:

An abnormal test finding will be classified as an *adverse event* if one or more of the following criteria are met:

The test finding is accompanied by clinical symptoms

The test finding necessitates additional diagnostic evaluation(s) or medical/surgical intervention; including significant additional concomitant drug treatment or other therapy

Note: simply repeating a test finding, in the absence of any of the other listed criteria, does not constitute an adverse event.

The test finding leads to a change in study drug dosing or discontinuation of subject participation in the clinical research study

The test finding is considered an adverse event by the Sponsor-Investigator of the IND application

8.2.2.2 Causality and severity assessment:

The Sponsor-Investigator of the IND application will promptly review documented adverse events and abnormal test findings to determine 1) if the abnormal test finding should be classified as an adverse event; 2) if there is a reasonable possibility that the adverse event was caused by the study drug(s); and 3) if the adverse event meets the criteria for a *serious adverse event*.

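### Section 5.1.1 offers leaving the trial, not just stopping study drug, for a serious condition, so a man withdrawn before day 90 has no scheduled post-baseline blood or urine panel and no end-of-treatment IPSS

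*Protocol*

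**What the plan says.** Section 5.1.1 is headed as a rule on non-compliance, but its text covers only one situation: "if any serious condition develops which requires urgent treatment such subject may be withdrawn from the trial and managed by the principal investigator accordingly". No other section says when a man is withdrawn, and none describes an early-termination visit.

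The surrounding provisions are these:

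- **Blinding (3.3).** There is none: "Blinding is not opted as both the trial drugs are classical preparations".
- **Rescue (5.5.2).** "If any problems occur, rescue medication will be governed by the investigators accordingly". This does not require withdrawal.
- **Primary outcome (6).** It is the "change in Total International Prostate Symptom Score from baseline to end of treatment".
- **IPSS schedule (6.1, Form III).** Clinical assessment is at days 0, 15, 30, 45, 60, 75 and 90. Form III as shown has rows for those days only.
- **Laboratory schedule (6.1, 7.1).** Blood and urine tests, which Section 7.1 makes the safety assessment, are done "before treatment (0 day), after treatment (at the end of 3rd 6th and 9th month".
- **Adverse events (8.2.2).** "For all adverse events, sufficient information will be pursued and/or obtained", and "Adverse events or abnormal test findings felt to be associated with the study drug(s) will be followed until the event" resolves or stabilises.
- **Sample size (3.2, 4, 6.4).** There are 10 men per arm and 20 in total. Section 4 expects twenty to be enrolled; the table in 6.4 says that the 20 does not include dropouts.

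**The concern.** The men covered by 5.1.1 are those who become seriously ill during treatment. Their illness may reflect treatment failure or toxicity, so whether they are measured may be related to their outcome. The rule is permissive, and whoever applies it in an open-label trial is likely to know the arm.

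The protocol does recognise that stopping drug and leaving the trial are different things. Section 8.2.2.1 lists a dosing change and the end of participation as alternatives, and 5.5.2 allows rescue without withdrawal. Section 5.1.1 does not use that distinction.

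A statistical analysis plan can say how missing values are handled. It cannot recover a blood sample or a symptom score that nobody took. Who is measured, and when, is settled in the protocol.

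**Working it through.** There is no figure in the protocol to reproduce: it states no dropout rate, effect size, standard deviation or power. The check sets the withdrawal rule against the schedules and counts what remains.

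**Assumption on timing.** The protocol gives treatment both as 12 weeks (12 × 7 = 84 days) and as three months. I take end of treatment to be the day 90 visit, the last one on Form III.

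**Step 1: blood and urine.** The scheduled times are day 0 and the end of months 3, 6 and 9. The number of scheduled panels after day 0 and before the end of month 3 is 0. A man withdrawn in that interval therefore has no scheduled post-baseline panel, whatever the day.

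**Step 2: IPSS.** There are 6 post-baseline visits (days 15, 30, 45, 60, 75, 90).

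| Day of withdrawal | IPSS visits kept | IPSS visits lost | Day 90 value |
|---|---|---|---|
| 0–14 | 0 | 6 | lost |
| 15–29 | 1 | 5 | lost |
| 30–44 | 2 | 4 | lost |
| 45–59 | 3 | 3 | lost |
| 60–74 | 4 | 2 | lost |
| 75–89 | 5 | 1 | lost |

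Up to five interim values may survive, but the value that Section 6 needs is missing in every row.

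**Step 3: share of an arm.** The text allows two readings of the sample size.

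- Exactly 10 enrolled per arm (Section 4): one man is 1/10 = 10%, two are 2/10 = 20%.
- Dropouts additional to the 20 (table in 6.4): one man is 1/11 = 9%, two are 2/12 = 17%.

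On the second reading 10 end-of-treatment values per arm are still reached, but they come from men who were not withdrawn.

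**Step 4: how often this could arise (illustration only).** For an assumed chance r of such a withdrawal per man, the chance of at least one in an arm of 10 is 1 − (1 − r)^10. This gives 40% for r = 5%, 65% for r = 10% and 89% for r = 20%. The rates are my assumptions, and nothing in the protocol favours one of them.

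**Step 5: what Section 8.2.2 still provides.** The event must be recorded, information on seriousness and causality pursued, and events thought to be drug-related followed. Under 8.2.2.2 a questionable relationship is classed as drug-associated for reporting. Unscheduled tests may therefore exist. None of these provisions schedules a panel or an IPSS.

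**The case against.** The strongest reply has four parts.

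- **The rule is permissive and silent on measurement.** It says a man may be withdrawn, leaves rescue and concomitant treatment open, and nowhere says that assessments stop. This stands as a limit: the loss follows from the plain meaning of being withdrawn from a trial, not from an explicit instruction to stop measuring. But no alternative is offered for the man who must stop drug, so the rule is fixed badly even though it contradicts nothing.
- **The decider is not named.** A reader might infer that the protocol gives the unblinded investigator the power to remove men. The sentence is passive and names only who manages the man afterwards. The investigator is the natural reading, no more. The missing data do not depend on it.
- **Safety is covered by Section 8.2.2.** A reader might infer that safety information on these men is lost. The text does not support that, since event-level information is secured. What is missing is mainly the scheduled panel. The lack of laboratory tests between day 0 and month 3 applies to all the men, but the others are tested at month 3.
- **A day-90 IPSS after urgent treatment is of uncertain value.** It partly reflects that treatment, and how to use it is an analysis question. This is fair, but the choice exists only if the value is collected.

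**Conclusion.** The point holds in this form. Section 5.1.1 offers withdrawal from the trial, does not separate it from stopping study drug, and provides no assessment at that point. A man withdrawn before day 90 then has no scheduled post-baseline blood or urine panel and no end-of-treatment IPSS, though 0 to 5 interim IPSS values and adverse-event information may exist. Each such man is about 9% to 10% of his arm, and two are 17% to 20%, depending on whether dropouts are additional to the 20. Replacement would restore the count but not the data lost from a selected group.

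A reader might go further and infer that the comparison is biased towards one arm. The documents do not support that. They give no withdrawal rate, a man relieved by urgent treatment could score better or worse at day 90, and similar losses in both arms could cancel.

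The conclusion rests on the plain meaning of withdrawal from a trial and on day 90 being the end of treatment. Form 4 and the complete case report form are not in the text available, so an assessment at stopping that appears only there would not have been seen. The change should be made, because it is cheap and the data cannot be recovered later.

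**What to change.** Amend Section 5.1.1 as follows:

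- Study drug may be stopped for a serious condition, and the man stays in the trial unless he withdraws consent. Say who takes the decision. His care remains with the investigator.
- When drug stops, do the Form 4 blood and urine tests and complete Form III, with IPSS where he can answer it. Add one row to Form III for this assessment.
- Record the days on drug and the date and type of urgent treatment.
- Continue the scheduled visits, including day 90.

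Days on drug matter because IPSS asks about the past month. Taking a month as 30 days, a score taken when drug stops on day d covers (30 − d)/30 of pre-treatment time: 67% at day 10, 50% at day 15, 33% at day 20 and none from day 30.

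The cost is a few sentences and one form row, some samples taken earlier than scheduled, and continued visits for the few men who stop. IPSS will not be answerable in some, for example with a catheter, and a day-90 score after urgent treatment will partly reflect that treatment. Recording the treatment lets the analysis take this into account.

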The current medical practice produces serious side effects such as Impotence, decreased libido, decreased quantity of semen at ejaculation, gynecomastia, asthenia, hypotension, dizziness, somnolence, fatigue, dyspnea and upper respiratory tract infection. When medication fails surgical intervention is needed but this is costly in practice. Moreover, at present herbal remedies like Saw Palmetto (*Serenoa repens*) produces good results in reducing the complaints of the BPH patients. Literary evidences reveal Siddha formulations are being practiced since ages. In exploring the efficacy of Siddha medication for this particular condition evaluation of a new investigational drug is indispensable.

1.2 Rationale:

The investigational new drug (IND) though a classical preparation, is going to be tested for new indication. So it falls under new chemical entity (NCE). Hence, as per AYUSH guidelines safety study is intended. The approval will be sought from the Institutional Animal Ethical Committee and the Safety studies will be done at Department of Pharmacology, SCRI, Chennai.

Another drug XXX is taken up for another one arm and its efficacy is compared with that of XXX. XXX is a well known Siddha drug and it is in practice since time immemorial. Its indication suits the clinical condition Neer kattu (Retention of urine). Since it is a classical drug which is going to be put into trial, preclinical study is not mandatory. [Ref: ICMR Guidelines& WHO Guidelines]

A sample size of twenty patients from OPD of CCRS Institutes will be randomized and put in two arms as open labeled study. The suitable participants as per inclusion criteria will be enrolled and the trial drugs will be administered orally as mentioned in the classical reference. The duration of the trial period will be three months.

BPH is a common condition that affects aged men. The prevalence of BPH is about 50% of men between 50 to 60 years and more than 90% of men who are older than 80 years old. However, only 25% of men above 50 and 50% of men above 75 are symptomatic.²

Benign prostatic hyperplasia (BPH) is a histological diagnosis that refers to the proliferation of smooth muscle and epithelial cells within the prostatic transition zone. It is the most common benign tumor in men and is not a precancerous condition.

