If the Sponsor-Investigator's final determination of causality is "unknown and of questionable relationship to the study drug(s)", the adverse event will be classified as *associated with the use of the study drug(s)* for reporting purposes. If the Sponsor-Investigator's final determination of causality is "unknown but not related to the study drug(s)", this determination and the rationale for the determination will be documented in the respective subject's case history.

9. Statistical methods/Data Analysis:

Clinical symptoms and Laboratory parameters will be analyzed using appropriate statistical method.

9.1 Study endpoints:

9.1.1 Primary endpoints:

- a) Measuring International Prostate Symptom Score
- b) Prostate Specific Antigen test

SYMPTOM SCORE - IPSS SCORE *

INTERNATIONAL PROSTATE SYMPTOM SCORE SHEET								
[name]:		Address:						
Patient Name:		Address:						
Date:						
Age Group:		40-49 	50-59 					
		60-69 	70+ 					
		Not at all	Less than 1 time in 5	Less than half the time	About half the time	More than half the time	Almost always	Your score
1. INCOMPLETE EMPTYING	Over the past month, how often have you had a sensation of not emptying your bladder completely after you finished urinating?	0	1	2	3	4	5	
2. FREQUENCY	Over the past month, how often have you had to urinate again less than two hours after you finished urinating?	0	1	2	3	4	5	
3. INTERMITTENCY	Over the past month, how often have you found you stopped and started several times when you urinated?	0	1	2	3	4	5	
4. URGENCY	Over the past month, how often have you found it difficult to postpone urination?	0	1	2	3	4	5	
5. WEAK STREAM	Over the past month, how often have you had a weak urinary stream?	0	1	2	3	4	5	
6. STRAINING	Over the past month, how often have you had to push or strain to begin urination?	0	1	2	3	4	5	
7. NOCTURIA	Over the past month, how many times did you most typically get up to urinate from the time you went to bed at night until the time you got up in the morning?	None 0	1 time 1	2 times 2	3 times 3	4 times 4	5 or more times 5	
Which of the above do you regard as most troublesome [1-7] _____								
TOTAL PROSTATE SYMPTOM SCORE _____								
		Delighted	Pleased	Mostly satisfied	Mixed - satisfied and dissatisfied	Mostly dissatisfied	Unhappy	Terrible

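### Twenty is both the number randomised and the number net of drop-outs; the two agree only if nobody leaves, and 5.1.1 does not provide for IPSS after withdrawal

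*Protocol*

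**What the plan says.** Five places in the protocol give the size of the trial.

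- Section 1.2 (Rationale): "A sample size of twenty patients from OPD of CCRS Institutes will be randomized and put in two arms as open labeled study".
- Section 3.2 (Allocation to treatment): "The sample size of subjects is 20. 10 subject each in a single arm".
- Section 4 (Subject selection): "The estimated total number of individuals to be enrolled in this clinical study will be twenty".
- Section 6 (Research Study Procedures) again describes a comparison in 20 patients.
- Section 6.4 (Study table), sample-size row: "20 [without including drop outs, lama", followed by ten subjects in each arm.

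No drop-out rate, over-enrolment number or replacement rule appears.

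Section 5.1.1 says that "if any serious condition develops which requires urgent treatment such subject may be withdrawn from the trial". It does not say whether IPSS is still recorded afterwards. Section 6 defines the primary outcome as "change in Total International Prostate Symptom Score from baseline to end of treatment", compared between the two drugs. Section 6.1 and Form III schedule clinical assessment, with IPSS on the form, on days 0, 15, 30, 45, 60, 75 and 90.

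**The concern.** The first four statements describe men entering the trial. The study table describes men left after drop-outs and those leaving against medical advice are taken out. A site following Section 4 would stop recruiting at twenty. A site following Section 6.4 would keep going until twenty had stayed, or would report on those who stayed as if they were the sample.

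Two things are at stake. One is size: if recruitment stops at twenty, ten per arm is not what the analysis will have. The other is validity. Both the man and the investigator know the treatment, so leaving can depend on the arm and on how the man is doing. A man withdrawn from the trial under 5.1.1 may also have no end-of-treatment IPSS. A statistical analysis plan cannot recover a score that was never collected, so this part has to be settled in the protocol.

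**Working it through.** **The plan's own figure.** The only arithmetic that can be reproduced is 2 × 10 = 20. The protocol gives no error rate, power, effect size, SD or drop-out rate, so twenty cannot be derived as either a gross or a net number. Loss rates below are assumptions.

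**Can both statements hold?** With N randomised and a fraction d leaving, N(1 − d) remain. If N = 20 and the remainder must also be 20, then d = 0. If each man leaves independently with probability d, the chance that nobody leaves is (1 − d)^20.

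| Assumed loss d | Expected completers, 20(1 − d) | Chance that all 20 complete |
|---|---|---|
| 5% | 19 | 0.95^20 = 36% |
| 10% | 18 | 0.90^20 = 12% |
| 20% | 16 | 0.80^20 = 1.2% |

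At 10% or more, the conflict would very probably arise in practice.

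**How many would have to enter for ten per arm to remain?** 10/(1 − d), rounded up: 10/0.9 = 11.1, so 12 per arm (24 in all) at 10% loss; 10/0.8 = 12.5, so 13 per arm (26 in all) at 20%. Neither number is in the protocol.

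**Precision.** For n per arm and a common SD, the 95% half-width for the difference in mean IPSS change is t(0.975; 2n − 2) × √(2/n) SD.

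- n = 10: 2.101 × √(2/10) = 0.94 SD
- n = 9: 2.120 × √(2/9) = 1.00 SD
- n = 8: 2.145 × √(2/8) = 1.07 SD

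The SD of IPSS change is not stated. If it were 6 points, the half-width would go from 5.6 to 6.4 points (n = 10 to n = 8). At 5 points it would go from 4.7 to 5.4, and at 7 points from 6.6 to 7.5.

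**Power, for scale.** With a two-sided 5% t-test, the difference detectable with 80% power is 1.33 SD at 10 per arm, 1.41 SD at 9 and 1.51 SD at 8. For an effect of 1.33 SD, power falls from 80% to 75% and then 69%.

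**Possible bias if leavers are not counted.** As a worst case, take an arm of ten with standard normal outcomes and no treatment effect, and remove its worst one, two or three men while the other arm loses nobody. In simulation, the arm's mean improves by about 0.17, 0.32 or 0.46 SD. If those doing best left, the shift would go the other way; if similar men left both arms, it would largely cancel.

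**The case against.** The strongest reply is that the bracket may mean only that no drop-out allowance was added. Read that way, Section 6.4 agrees with the other four places. This is possible but strained: the words attach to the count of 20 and say who is not included in it. Section 4 also calls its number an estimate, so enrolling more than twenty is not ruled out. However, Section 1.2 carries no such qualifier, and no larger number is given anywhere.

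A reader might infer that 5.1.1 removes men whose symptoms worsen, so that treatment failures drop out of the twenty. The text does not say that. It is permissive, it concerns any serious condition needing urgent treatment, and it mentions neither IPSS nor lack of efficacy. An unrelated emergency would qualify and ordinary worsening would not. What stands is narrower: such conditions may include complications of BPH, since the protocol's background itself names acute urinary retention and need for surgery among the things treatment can affect.

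A reader might also infer that outcome collection stops at withdrawal, or that the analysis is restricted to completers. Neither is stated. Section 5.1.1 is silent on later data, and nothing says that scores already recorded are discarded. Section 8.2.2 continues follow-up of adverse events and test findings thought to be drug-related, but that does not cover IPSS. Section 9 says only that "Clinical symptoms and Laboratory parameters will be analyzed using appropriate statistical method". An analysis set may properly be defined in a statistical analysis plan that is not shown, and its absence here is no fault.

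Finally, the loss of precision is modest, and the protocol sets no power or precision target that 8 per arm would miss. That is fair.

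**Conclusion.** The point holds in a limited form. Section 6.4, on its natural reading, contradicts Sections 1.2 and 4: the stated ten per arm is not delivered once anyone leaves, unless more men are entered than the protocol says. At an assumed 10 to 20% loss, 18 to 16 men complete, and the half-width rises from 0.94 SD to at most 1.07 SD if losses are equal between arms.

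Attrition bias is a risk, not a stated feature. It arises if 6.4 is applied by not counting men who leave, and it is made likelier by open treatment and by the lack of any provision for IPSS after withdrawal. Its direction and size depend on who leaves; the 0.17 to 0.46 SD above is a one-sided worst case. With ten men per arm, each is a tenth of his arm's result, so the matter should be settled before recruitment.

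**What to change.** 1. Reconcile Sections 1.2, 3.2, 4, 6 and 6.4. In 6.4, delete the bracket and state that 20 men are randomised, 10 per arm; that fewer may complete; and that every randomised man counts in the arm to which he was assigned.
2. In 5.1.1, leave the clinical decision with the investigator, unchanged, but distinguish stopping study drug from leaving the study. Where the man agrees, continue IPSS at the planned visits to day 90 after study drug stops.
3. Describe any analysis of completers as a sensitivity analysis only.

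This makes the stated number true; it does not make it larger. If the sponsor wants ten completers per arm, a larger randomised number with its assumed loss rate has to be stated instead, and all randomised men still counted.

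The cost is a few sentences, a few more Form III assessments at visits already planned, and a slightly less favourable number of completers on paper.
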